1.2. INFORMATION ON THE TEST PRODUCT

1.2.1. ENCORAFENIB

Chemical and pharmaceutical characteristics

Encorafenib (LGX818 or W0090), is a novel oral small-molecule kinase inhibitor with potent and selective inhibitory activity against mutant *BRAF* kinase, a member of the RAF/MEK/ERK MAPK pathway, which plays a prominent role in controlling several key cellular functions including growth, proliferation and survival.

For further details, please refer to the current Encorafenib Investigator's Brochure (**Enco IB**).

Non-clinical data

In 1- to 4-week toxicology studies in rats and cynomolgus monkeys, encorafenib was well tolerated at systemic exposures which result in tumor regression in mouse xenograft studies. Findings included hyperplasia and hyperkeratosis in the skin (plantar surface of feet) and non-glandular stomach in the rat. An absence of the later stages of spermatid maturation in male rats was also observed. Significant mortality/morbidity was observed mostly in female rats at the highest dose of 400 mg/kg/day, a dose well above the maximum tolerated dose (MTD) in rats.

In the 13-week toxicology study in monkeys, the only drug-related finding was blister-like lesions identified over the macular region of the retina, observed in 2 monkeys treated at a dose of 60 mg/kg/day. Exposure (maximum area under the concentration–time curve (AUC)₀₋₂₄ achieved in the study at any time point) in the 2 affected monkeys was 5 to 8-fold and 4 to 6-fold greater than that achieved at the 300 and 450 mg once daily (QD) dose levels, respectively, in humans at steady state in Clinical Study CLGX818X2101. One of the animals with this finding showed evidence of recovery after the drug withdrawal. Histopathology examination of the affected eyes suggested that the findings were similar to the retinopathy associated with MEK inhibitors.

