5.7.1. Treatment Discontinuation for Individual Subject

Subjects may decide to stop participating in the study at any time for any reason without prejudice to their future medical care by the physician or at the institution. Wherever possible, the tests and evaluations listed for the End of Treatment visit and Safety Follow-up visit should be carried out and an effort should be made to continue follow-up.

If a subject decides to discontinue study treatment, he/she should be asked if he/she is willing to be contacted by telephone for monitoring of survival.

If a subject withdraws consent, the subject's data collected up to the date of consent withdrawal will be included in the analyses. The date, stated reason for and level of consent withdrawal should be documented. Any blood or tissue samples collected up to the date of withdrawal of consent will be analyzed, unless explicitly prohibited by the subject.

The Sponsor should be notified of all subjects' decision to discontinue study treatment and all study withdrawals through the designated e-CRFs in a timely manner.

Subjects meeting any of the following criteria must discontinue study drug treatment:

- **Subject decision to discontinue study treatment** (but request agreement to return for end of treatment assessments, safety follow-up assessments and/or survival follow-up).
- **Withdrawal of consent:** no further participation
- **Lost to follow up:** A subject will be considered as lost to follow up, if he/she did not attend a scheduled visit and for whom no news can be obtained after three documented attempts

with a minimum of 15 days between the first and the last attempt. This status must be dated at the latest as the database lock.

- **Investigator decision** in the subject's interest if an SAE occurs and is considered by the Investigator liable to threaten the health of the subject or if a serious disease occurs and necessitates the prescription of a medication incompatible with the pursuit of the study. The Sponsor should immediately be informed by phone or fax or email and a report explaining the discontinuation will be forwarded to him as soon as possible.
- **Progressive disease:** at any time (to be taken into account only for treatment discontinuation).
- **Unacceptable AE or toxicity** (related or not to the study treatment) or failure to tolerate the study treatment.

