6.5.4. Dose Modification

Subjects will be monitored for AEs. The severity of AEs will be evaluated using the NCI-CTCAE v.4.03.

If a subject develops toxicity, the dose should be modified as outlined in **Table 14** and **Table 15**, which include criteria for interruption and reduction of encorafenib, binimetinib and cetuximab. All dose modifications should be based on the worst preceding toxicity. All dosing interruptions and modifications must be recorded in the e-CRF.

If a subject permanently discontinues binimetinib due to an AE or clinically significant laboratory value, they may continue to receive encorafenib in combination with cetuximab.

Due to the lack of efficacy of binimetinib, encorafenib, or cetuximab when used as single agents in subjects with *BRAF*-mutant mCRC, subjects who cannot tolerate these agents in combination with at least one other agent, should discontinue study treatment altogether, complete the end of treatment visit and continue to be followed for survival (and disease progression, if applicable).

Cetuximab may be reduced by 2 dose levels to a minimum of 150 mg/m², due to AEs or laboratory abnormalities (**Table 8**). When a dose reduction is required because of an AE, no subsequent dose re-escalation of cetuximab will be permitted for that subject for the duration of study treatment. If after resolution of an AE, treatment is resumed at the same dose, and the same toxicity reoccurs with the same severity, any re-initiation of treatment must be at the next lower dose level irrespective of duration, with some exceptions for skin toxicity.

In addition, a subject must discontinue study treatment if, after treatment is resumed at a lower dose of cetuximab, the same toxicity reoccurs with the same or worse severity.

If a subject misses > 28 consecutive days of encorafenib or binimetinib, or > 4 consecutive cetuximab doses as the result of an AE or clinically significant laboratory abnormality, then the respective agent(s) should be discontinued.

Subjects who discontinue study treatment for a study-related AE or an abnormal laboratory value must complete the end of treatment visit and continue to be followed for survival (and disease progression).

Table 8: Dose Levels for Dose Modification

	Encorafenib (mg QD)	Binimetinib (mg BID)	Cetuximab WEEKLY (mg/m²)	Cetuximab BI-WEEKLY (mg/m²) Starting from C8D1 week 29 Or at any cycle since implementation of the Urgent Safety Measure on 26 Mar 2020

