6.5.4.1. Dose Modification for Encorafenib and/or Binimetinib

Doses of encorafenib and/or binimetinib may be adjusted for AEs throughout the study as described in Table 14. In general, doses should not be reduced or interrupted for Grade 1 AEs other than for specific ocular AEs referred to in **Table 13**, but treatment to control symptoms should be provided as appropriate, if applicable.

An individual subject may have their dose of encorafenib and/or binimetinib reduced to the dose levels specified in **Table 8**.

The lowest permitted dose level of encorafenib is 150 mg QD and the lowest permitted dose level of binimetinib is 15 mg BID.

If the AE causing a dose reduction improves to the subject's Baseline level and remains stable for a minimum of 14 days, the dose can be re-escalated to the next dose level at the discretion of the Investigator, provided there are no other concomitant toxicities that would prevent drug re-escalation. There is no limit to the number of times the subject can have their dose reduced or re-escalated (in increments specified in **Table 8**).

- No dose re-escalation of encorafenib is allowed after a dose reduction due to prolonged QTcF ≥ 501 msec
- No dose re-escalation of binimetinib is allowed after a dose reduction due to LVEF dysfunction or prolonged QTcF ≥ 501 msec
- No dose re-escalation of binimetinib or encorafenib is allowed after a dose reduction due to retinal toxicity \geq Grade 2.

Refer to **Table 14** for recommended dose modifications for encorafenib and/or binimetinib, if applicable, based on the occurrence of treatment-related AEs.

Eye disorders that cannot be specifically graded according to modified NCI-CTCAE, v.4.03, should be graded according to **Table 9**. Serous detachment of the retina should be graded according to **Table 10**.

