Uveitis should be graded according to NCI-CTCAE, v.4.03 as described in **Table 11**, Hand-foot skin reactions (HFSR) should be graded according to NCI-CTCAE, v.4.03 as described in **Table 12**. Diarrhea should be graded according to modified NCI-CTCAE, v.4.03 as described in **Table 13**. Furthermore, please refer to **Section 17.1** for additional supportive care recommended guidelines for the management of: cetuximab-induced, encorafenib-induced and/or binimetinib-induced skin reaction (**Section 17.1**), encorafenib-induced HFSR (**Section 17.2**), binimetinib-induced diarrhea (**Section 17.3**) and binimetinib-associated interstitial lung disease/pneumonitis (**Section 17.7**).

Table 9: Modified NCI CTCAE, Version 4.03 Grading of Eye Disorders

Grade	Description
1	Asymptomatic or mild symptoms; clinical or diagnostic observations only; intervention not indicated
2	Moderate; minimal, local or noninvasive intervention indicated; limiting age-appropriate instrumental activities of daily living
3	Severe or medically significant but not immediately sight threatening; hospitalization or prolongation of existing hospitalization indicated; disabling; limiting self-care activities of daily living
4	Sight-threatening consequences; urgent intervention indicated; blindness (20/200 or worse) in the affected eye

Table 10: NCI CTCAE, Version 4.03 Grading of Serous Detachment of the Retina

Grade	Description
1	Asymptomatic (but with findings in ocular coherence tomography, fundoscopy and/or slit lamp biomicroscopy)
2	Symptomatic with moderate decrease in visual acuity (20/40 ^a or better); limiting instrumental activities of daily living
3	Symptomatic with marked decrease in visual acuity (worse than 20/40 ^a); limiting self-care activities of daily living
4	Blindness (20/200a or worse) in the affected eye

Note: For rhegmatogenous retinal detachment, grade according to NCI-CTCAE v.4.03 Retinal Detachment. a Please refer to (**Section 17.3**).

Table 11: NCI CTCAE, Version 4.03 Grading of Uveitis

Grade	Description
1	Asymptomatic; clinical or diagnostic observations only
2	Anterior uveitis; medical intervention indicated
3	Posterior or pan-uveitis
4	Blindness (20/200 ^a or worse) in the affected eye

a Please refer to (**Section 17.3**).

Table 12: NCI CTCAE, Version 4.03 Grading of Hand-foot Skin Reaction (HFSR)^a

Grade	Description ^b

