Grade 1	Maintain dose levels of encorafenib and binimetinib and repeat ophthalmic monitoring including visual acuity assessment and OCT within 10 days. 
 If subject remains asymptomatic (Grade 1), maintain dose level of encorafenib and binimetinib and continue the schedule of visual assessments established per protocol. If subject becomes symptomatic (blurred vision, photophobia, etc.) or visual acuity assessment shows Grade 2, follow Grade 2 dose guidelines below.
Grade 2	Interrupt dosing of encorafenib and binimetinib and repeat ophthalmic monitoring including visual acuity assessment and OCT within 10 days. 
 If resolved to baseline or Grade ≤ 1, resume treatment at current dose level of encorafenib and binimetinib and continue the schedule of visual assessments established per protocol. If not resolved to baseline or Grade ≤ 1, resume treatment at 1 reduced dose level^b of encorafenib and binimetinib and continue the schedule of visual assessments established per protocol.
Grade 3	Interrupt dosing of encorafenib and binimetinib and repeat ophthalmic monitoring including visual acuity assessment and OCT within 10 days: 
 If resolved to baseline or Grade ≤ 2, resume treatment at 1 reduced dose level^b of encorafenib and binimetinib and continue the schedule of visual assessments established per protocol. If not resolved to baseline or Grade ≤ 2, continue the interruption and repeat the ophthalmic assessment in 10 days. 
 If resolved to baseline or Grade ≤ 2, resume treatment at 1 reduced dose level^b of encorafenib and binimetinib and continue the schedule of visual assessments established per protocol If remains Grade 3, permanently discontinue encorafenib and binimetinib.
Grade 4	Permanently discontinue binimetinib and immediate follow-up with ophthalmic monitoring ^c .

Worst toxicity CTCAE, v.4.03 Grade (unless otherwise specified ^a)	Dose Modification for Encorafenib and for Binimetinib
Eye Disorders - Posterior Uveitis^c Note: Results and images of ocular coherence tomography (OCT) must be made available upon request. Any visual acuity impairment at screening should be documented and should be considered as baseline.	

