Grade 1	Maintain dose levels of encorafenib and binimetinib and repeat ophthalmic monitoring including visual acuity assessment and OCT within 10 days. 
 If subject remains asymptomatic (Grade 1), maintain dose level of encorafenib and binimetinib and continue the schedule of visual assessments established per protocol. If subject becomes symptomatic (blurred vision, photophobia, etc.) or visual acuity assessment shows Grade 2, follow Grade 2 dose guidelines below.
Grade 2	Interrupt dosing of encorafenib and binimetinib and repeat ophthalmic monitoring including visual acuity assessment and OCT within 10 days. 
 If resolved to baseline or Grade ≤ 1, resume treatment at current dose level of encorafenib and binimetinib and continue the schedule of visual assessments established per protocol. If not resolved to baseline or Grade ≤ 1, resume treatment at 1 reduced dose level^b of encorafenib and current dose of binimetinib and continue the schedule of visual assessments established per protocol. If posterior uveitis lasts > 6 weeks, permanently discontinue binimetinib and encorafenib.
Grade 3	Interrupt dosing of encorafenib and binimetinib and repeat ophthalmic monitoring including visual acuity assessment and OCT within 10 days: 
 If resolved to baseline or Grade ≤ 2, resume treatment at 1 reduced dose level^b of encorafenib and current dose of binimetinib and continue the schedule of visual assessments established per protocol. If not resolved to baseline or Grade ≤ 2, continue the interruption and repeat the ophthalmic assessment in 10 days. If remains Grade 3, permanently discontinue encorafenib and binimetinib.
Grade 4	Permanently discontinue encorafenib and binimetinib and immediate follow-up with ophthalmic monitoring ^c .
Eye Disorder - RVO^c(Retinal Vein Occlusion) Note: Results and images of ophthalmic examinations should be made available upon request. This includes scans/images of fluorescein angiography should a subject be assessed using this technique.	
RVO of any grade	Permanently discontinue binimetinib and immediately follow-up with ophthalmic monitoring ^c .
Other Eye Disorders (i.e., Non-Retinal Events)	
Grade 1 – 2	Maintain dose level of encorafenib and binimetinib and increase frequency of ophthalmic monitoring to at least every 14 days until stabilization or resolution.

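### For a Grade 4 retinal event, Table 14 stops binimetinib only, so encorafenib may continue at blindness although Grades 2 and 3 interrupt it

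*Protocol*

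**What the plan says.** The action column of Table 14 (Protocol Section 6.5.4.1) covers encorafenib and binimetinib together. In the Retinal Events block:

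- Grade 1: both drugs continue, with repeat ophthalmic assessment.
- Grade 2: both are interrupted, then resumed at the current or a reduced dose.
- Grade 3: both are interrupted. They resume one level lower on recovery to baseline or Grade 2 or better. Otherwise: "If remains Grade 3, permanently discontinue encorafenib and binimetinib".
- Grade 4: "Permanently discontinue binimetinib and immediate follow-up with ophthalmic monitoring".

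For serous retinal detachment, Table 10 defines Grade 4 as "Blindness (20/200a or worse) in the affected eye".

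For subjects who permanently stop binimetinib because of an adverse event, Section 6.5.4 states that "they may continue to receive encorafenib in combination with cetuximab". Section 5.7.1 lists "Unacceptable AE or toxicity" among the reasons for which study drug must be stopped. Section 4.1 carries the same dose-modification recommendations into the extension period.

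**The concern.** A dose-modification table should not become more permissive as a toxicity worsens. Here the instruction for encorafenib tightens from Grade 1 to persistent Grade 3 and then disappears at Grade 4. The general rule in Section 6.5.4 fills that gap in the permissive direction.

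A site following the row literally could keep giving encorafenib to a subject who has lost vision in an eye, when a milder event would have required a hold.

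The protocol itself links encorafenib to the retina. Section 6.5.4.1 says "No dose re-escalation of binimetinib or encorafenib is allowed after a dose reduction due to retinal toxicity" of Grade 2 or more. Section 1.2.1 reports, for the 13-week monkey study of encorafenib, that "the only drug-related finding was blister-like lesions identified over the macular region of the retina". What is at stake is subject safety and a clear instruction to sites, not the efficacy inference.

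**Working it through.** The protocol gives no figure to reproduce. The check sets the rows side by side.

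**Step 1. Action on encorafenib by retinal grade**

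| Grade | Binimetinib | Encorafenib |
|---|---|---|
| 1 | maintain | maintain |
| 2 | interrupt; resume at same or lower dose | same |
| 3, recovering | interrupt; resume one level lower | same |
| 3, persisting | stop permanently | stop permanently |
| 4 | stop permanently | no instruction; Section 6.5.4 permits continuation |

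The reversal occurs in the last row and only for encorafenib.

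**Step 2. Does another rule close the gap?**

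- Table 14 footnote c, attached to the row, concerns ophthalmic imaging only.
- Footnote f (conditional resumption after a Grade 4 event) is not attached to this row and would loosen the rule, not tighten it.
- The Grade 4 row for all other adverse events stops both drugs, but retinal events have their own block.
- Section 5.7.1 requires stopping for unacceptable toxicity, but names no eye grade and depends on judgement.

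**Step 3. Comparison with the rest of Table 14.** Take the blocks that have a separate Grade 4 row and also interrupt encorafenib at a lower grade.

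| Block | Grade 4 action |
|---|---|
| Retinal events | stop binimetinib only |
| Posterior uveitis | stop both |
| Other eye disorders | stop both |
| Liver | stop both |
| Rash | stop both (footnote f) |
| Nausea/vomiting | stop both (footnote f) |
| All other adverse events | stop both (footnote f) |

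Count: 7 blocks, of which 6 stop both drugs (3 of the 6 allow conditional resumption under footnote f) and 1 does not.

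Blocks left out of this count:

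- Left ventricular dysfunction, hand-foot skin reaction and skin lesions: headed as single-drug.
- CK elevation without renal impairment: encorafenib is explicitly maintained at Grades 3 and 4.
- CK elevation with renal impairment, and diarrhea: Grades 3 and 4 share one row that acts on both drugs.
- QTcF: not organised by grade.
- Retinal vein occlusion: one row for any grade.
- Interstitial lung disease: encorafenib is maintained at Grades 1 and 2.

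**Step 4. A wider count.** Leaving out only the single-drug blocks and QTcF gives 12 blocks that cover a Grade 4 event. Four of these act on binimetinib without stopping encorafenib: retinal events, retinal vein occlusion, CK elevation without renal impairment, and interstitial lung disease. In the last three, encorafenib is not restricted at any lower grade, so nothing is reversed. Among these four, only the retinal block restricts encorafenib at lower grades and then drops the restriction at Grade 4.

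**Step 5. Wording of neighbouring rows.** The Grade 4 row for posterior uveitis, in the next block, reads "Permanently discontinue encorafenib and binimetinib and immediate follow-up with ophthalmic monitoring". It differs from the retinal row only in naming encorafenib. Where Table 14 means one drug, it often says so, as in the heading for left ventricular dysfunction and the CK rows.

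**The case against.** The strongest case is that the row may be deliberate. The protocol presents retinal events mainly as a MEK-inhibitor toxicity. Section 1.2.2 lists them among the relevant toxicities of binimetinib, and Table 4 shows retinal detachment in 14% of subjects on that drug alone. The monkey lesions were judged similar to MEK-inhibitor retinopathy, occurred in 2 animals at 5 to 8 times the human exposure at 300 mg, and showed evidence of recovery in one. Retinal vein occlusion and Grade 3-4 interstitial lung disease also name binimetinib alone without a single-drug label. Intent therefore cannot be excluded. It still would not explain why persistent Grade 3 stops both drugs.

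Second, the exposure is narrow:

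- A subject who worsens through Grade 3 already has encorafenib on hold, and the Grade 4 row does not say to resume it. The gap clearly applies to a subject taking encorafenib when Grade 4 is first found.
- Section 6.5.4 permits continuation and does not require it. Section 5.7.1 would lead most investigators to stop.
- Table 14 is framed as recommendations, although Section 6.5.4 directs sites to modify doses according to it.
- The last enrolled subject started treatment on 27 Dec 2019, before protocol version 9.0 (17 Jul 2020), so only subjects still on treatment are affected.

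These points stand. They limit how often the row matters, but they do not remove the inconsistency.

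**Conclusion.** The concern holds as stated. The text is unambiguous: encorafenib is interrupted at retinal Grades 2 and 3, stopped at persistent Grade 3, and left without instruction at Grade 4, where Section 6.5.4 allows it to continue. Under the Step 3 criteria, this is the one block of 7 that does not stop both drugs at Grade 4.

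That the row is a slip is an inference from the neighbouring rows. Confidence in that inference is medium, because a binimetinib-only rule cannot be ruled out. The row needs correcting on either reading, since a deliberate exception would also have to be stated.

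The protocol does not give the number of Grade 4 retinal events to expect in this trial, and it is assumed to be small. Table 4 offers only a loose yardstick, from another tumour type and one drug: 39 of 269 subjects had Grade 1-2 retinal detachment and none had Grade 3 or 4. The confirmed response rate, type I error and power are not affected. The reason to act is subject safety.

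**What to change.** Change the Grade 4 row of the Retinal Events block to "Permanently discontinue encorafenib and binimetinib and immediate follow-up with ophthalmic monitoring", keeping footnote c. This aligns it with persistent Grade 3 retinal events and with Grade 4 posterior uveitis and other eye disorders.

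If the sponsor does intend encorafenib to continue, the row should say so and give the dose, the conditions and the reason. The other eye-disorder blocks need no change.

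The cost is one table row. Section 15.1 makes every protocol change subject to a signed amendment, and substantial ones go to ethics committees and competent authorities, so the row is best carried in the next amendment. An interim clarification letter could alert the approximately 70 centers if the sponsor's procedures allow it.

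### Posterior uveitis that becomes symptomatic is Grade 3 by Table 11, but Table 14 sends it to a Grade 2 row with a different restart dose and stopping rule

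*Protocol*

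**What the plan says.** **Grading.** Protocol Section 6.5.4.1 says "Uveitis should be graded according to NCI-CTCAE, v.4.03 as described in" Table 11. In that table Grade 1 is asymptomatic, Grade 2 is "Anterior uveitis; medical intervention indicated", Grade 3 is "Posterior or pan-uveitis", and Grade 4 is blindness in the affected eye.

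**Dosing.** The first column of Table 14 is headed "Worst toxicity CTCAE, v.4.03 Grade (unless otherwise specified", with footnote a marking the exceptions. In the Posterior Uveitis block, the Grade 1 row keeps both drugs at dose and repeats the eye examination within 10 days. It then adds: "If subject becomes symptomatic (blurred vision, photophobia, etc.) or visual acuity assessment shows Grade 2, follow Grade 2 dose guidelines below". The Grade 2 row sets a time limit: "If posterior uveitis lasts > 6 weeks, permanently discontinue binimetinib and encorafenib". The Grade 3 row ends with: "If remains Grade 3, permanently discontinue encorafenib and binimetinib".

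**General rules.** Section 6.5.4 states: "All dose modifications should be based on the worst preceding toxicity". Section 4.1 carries the same dose-modification recommendations into the study extension.

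**The concern.** Two instructions in the same section classify the same eye differently. By Table 11, a subject with posterior uveitis who develops symptoms is Grade 3. By the Grade 1 row of Table 14, that subject is handled as Grade 2. Nothing in the protocol says which prevails, and the rows differ on the encorafenib dose at restart, on whether drug is given while the uveitis is unresolved, and on when treatment ends for good.

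At stake are the safety of subjects with a sight-threatening toxicity and consistent dosing across sites. Two investigators who both follow the protocol could treat the same subject differently.

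**Working it through.** **Step 1: which grade applies.** On Table 11, asymptomatic posterior uveitis is Grade 1. Once symptomatic it cannot be Grade 1, it is not anterior uveitis, and short of blindness it is not Grade 4. It is Grade 3. The second trigger in the Grade 1 row, a visual acuity finding of Grade 2, has no anchor either, because Table 11 has no acuity criterion for Grade 2. The same sentence appears in the Retinal Events block, where it works: Table 10 defines a symptomatic, acuity-based Grade 2.

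**Step 2: what each row does.** Both rows interrupt both drugs and re-examine within 10 days. Then:

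| State | Grade 2 row | Grade 3 row |
|---|---|---|
| Resolved at first check | Both drugs at current dose | Encorafenib one level lower, binimetinib at current dose |
| Not resolved at first check | Restart both, encorafenib one level lower | Stay off both, re-examine in 10 days |
| Permanent stop | Uveitis lasting more than 6 weeks | Still Grade 3 at second check |

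From Table 8, one encorafenib level is (300 − 225)/300 = 25% from the starting dose, or (225 − 150)/225 = 33% from the next level.

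**Step 3: timing for an unresolved event.** Let k be the days of uveitis before interruption and c the day of the first check after interruption (c at most 10). The documents give no value for k, so it is an assumption. The Grade 2 instruction addresses a subject already managed as Grade 1, so k > 0.

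- Dosing with unresolved uveitis under the Grade 2 row: 42 − k − c.
- Permanent stop under the Grade 3 row: day c + 10, that is day 20 for c = 10.
- Delay of the stop under the Grade 2 row: (42 − k) − (c + 10) = 32 − k − c.

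| k | c | Days dosed while unresolved | Later stop (days) |
|---|---|---|---|
| 10 | 10 | 22 | 12 |
| 10 | 5 | 27 | 17 |
| 20 | 10 | 12 | 2 |
| 22 | 10 | 10 | 0 |

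These are upper bounds: they assume no further interruption and no stop for another reason.

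**Step 4: does another rule settle it?**

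- Worst preceding toxicity (Section 6.5.4) favours the Grade 3 row but does not cancel the explicit direction to the Grade 2 row.
- The 28-day limit on missed doses (Sections 5.7.1 and 6.5.4) is not reached: about 10 days are missed under the Grade 2 row and about 20 under the Grade 3 row.
- Table 9 is reserved by Section 6.5.4.1 for eye disorders without a specific grading. Uveitis has one.
- If the block is read as setting its own scale, Grade 2 means symptomatic and nothing defines entry to the Grade 3 row.

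**The case against.** The best defence is that Table 14 gives recommendations, that both rows take the urgent step of interrupting both drugs and re-examining within 10 days, and that Section 5.7.1 still requires stopping for unacceptable toxicity. This limits the harm, and it is why the day counts are upper bounds. It does not remove the conflict, because Section 6.5.4 says doses should be modified as Tables 14 and 15 set out.

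Some stronger readings are tempting but not supported:

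- A reader might take k = 0 and infer 32 days of dosing and a 22-day delay. The explicit Grade 2 direction covers only a subject already managed as Grade 1, so uveitis predates the interruption. A subject first seen with symptomatic posterior uveitis is Grade 3 by Table 11, and no text sends that subject to the Grade 2 row.
- A reader might call the Grade 3 recovery test (baseline, or Grade 2 or lower) incoherent because Grade 2 means anterior uveitis. Grade 3 includes pan-uveitis, and clearance of the posterior part with residual anterior uveitis is a genuine move to Grade 2.
- A reader might infer that the encorafenib reduction can never be reversed. Section 6.5.4.1 bars re-escalation after retinal toxicity of Grade 2 or higher. Section 8.3.6 lists posterior uveitis among retinal abnormalities, but footnote c of Table 14 lists it separately from retinal events. The point is unsettled.
- A reader might treat the absence of footnote a as proof that strict CTCAE grading was meant. Footnotes are used unevenly: the diarrhea block relies on the modified grading of Table 13 without footnote a. The case rests on Section 6.5.4.1 and Table 11, not on the footnote.

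The event is probably uncommon. Uveitis is not listed in Table 5 (terms in at least 10%; N = 274 and 257 on encorafenib plus binimetinib) or Table 6 (at least 15%; N = 30 on the triplet). That is only a loose ceiling, so the number of subjects affected cannot be estimated.

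**Conclusion.** The conflict stands for one defined group: subjects managed as Grade 1 posterior uveitis who become symptomatic. For them the protocol gives two dosing paths. Resolution at the first check means either no change or a 25% encorafenib reduction from the starting dose. Non-resolution means either restart or continued interruption with a permanent stop at about day 20. With k = 10 and c = 10, both assumed, the Grade 2 row allows up to about 22 days of dosing with unresolved uveitis and a stop up to about 12 days later. The existence of the conflict does not depend on those values.

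The scope is patient safety and uniform dosing for subjects still on treatment, including the extension. The primary endpoint and sample size are not affected. It should be corrected.

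**What to change.** Use one scale in the Posterior Uveitis block, by either route:

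- **(a) Follow Table 11.** Change the Grade 1 row so that a subject who becomes symptomatic follows the Grade 3 row, and delete the Grade 2 row. Keep the Grade 3 recovery test at baseline, or Grade 2 or lower; residual anterior uveitis then falls under Other Eye Disorders, where Grade 1-2 means maintaining dose. Tightening the test to Grade 1 would leave residual anterior uveitis with no rule at the second check. Add a branch for recovery at the second check, which the Retinal Events Grade 3 row has and this row lacks. State whether the 6-week limit is kept.
- **(b) Define a dosing scale.** Mark the block with footnote a and give the symptom and acuity criteria for entry to its Grade 2 and Grade 3 rows, with adverse event grades still recorded by Table 11.

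The clinical content of each row is for the sponsor to decide. The cost is the wording of one block of Table 14 and a notice to sites on any ongoing case. The last enrolled subject started on 27 Dec 2019, so the benefit is confined to subjects still on treatment.
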